4 DEFINITIONS AND DATA CONVENTIONS

Body Mass Index (BMI)

BMI will be computed using the following formula:

$$\text{BMI} = \text{Body Weight (kg)} / (\text{Height (m)})^2$$

Daily dosage

Daily dosage (mcg) will be computed for each patient as:

$$\text{Daily Dosage} = \left(\frac{\sum_{i=1}^7 (\text{daily dosage}_i [\text{mcg}])}{7} \right)$$

where “i” is the day of the week.

Daily dosage/Body Weight

Daily dosage/Body Weight (mcg / kg) will be computed for each patient as:

$$\text{Daily Dosage/Body Weight} = \frac{\left(\frac{\sum_{i=1}^7 (\text{daily dosage}_i [\text{mcg}])}{7} \right)}{\text{Weight [kg]}}$$

where “i” is the day of the week.

Previous medications

Medications reported with an end date before the first study treatment administration (end date < date of first study treatment administration).

Concomitant medications

Medications reported as ongoing or with an end date after the first study treatment administration (ongoing or end date ≥ date of first study treatment administration). Any medications with an unknown end date will be assumed to be concomitant medications.

Treatment-Emergent Adverse Events (TEAEs)

Treatment-Emergent Adverse Events are defined as follows:

- Adverse events which started on or after the first study treatment administration.
- Adverse events without start date and with an end date after the first study treatment administration.
- Adverse events without start date and reported as ongoing (for subjects who take at least one dose of study treatment).

Pre-Treatment Adverse Events (PTAEs)

Adverse events which start before the first study treatment administration (start date < date of first study treatment administration).

Serious Adverse Events (SAEs)

Adverse Event assessed as serious.

Drug related Adverse Events

Adverse Events with a relationship to treatment reported as "Certain", "Probable" or "Possible".

Adverse events leading to discontinuation

Adverse Events leading to discontinuation is an AE with action taken equal to "Drug withdrawn".

Adverse events leading to death

Adverse Events leading to death is an AE with outcome equal to "Fatal".

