## **14 DISCONTINUATION/WITHDRAWAL**

### **14.1 DISCONTINUATION/WITHDRAWAL**

Participation will be discontinued for any of the following reasons:

- Voluntary subject/legally authorized representative withdrawal for any reason;
- PI's discretion;
- An AE, including onset or worsening of a concomitant illness, that is considered by the PI to be incompatible with continuation in the study;
- Administration of a drug that is not permitted according to the exclusion criteria;
- Failure to comply with the requirements of the protocol or major protocol deviation (e.g., inclusion error, evidence of noncompliance with exclusion/inclusion criteria during the study, subject misses study visits, failure to take assigned medication, or provide blood sample as required, etc.);
- Lost to follow-up; or
- Subject death.

Subjects whose parents or legal guardians provide informed consent, receive the IP and subsequently withdraw, or are withdrawn or discontinued from the study, will not be replaced.

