#### **16.2.15 END OF STUDY (EOS) VISIT:**

The EOS visit should be performed at Visits 8 through 11 according to the age of inclusion outlined in [Table 2](#).

At the EOS the PI will prescribe the appropriate LT4 product to allow continuation of TH therapy, upon presentation to parents of the possible alternatives and questioning about their preferential choice.

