### **19.3.4 SAFETY OUTCOMES**

Vital signs at each in-person visit will be analyzed descriptively within treatment groups.

Length, weight and head circumference will be analysed at each in-person visit by means of basal value, treatment group, newly diagnosed neonates vs infants already on LT4 therapy, age at inclusion and center as covariate.

The presence of signs and symptoms of hypo- and hyper-thyroidism at each planned visit will be compared between treatment groups by means of Chi test.

Number of subjects experiencing AEs and SAEs during the study will be calculated. Number of AEs and SAEs will also be calculated. Difference between treatment groups on subjects who experienced AEs and SAEs will be evaluated using a Chi test or a two-tailed Fisher's exact test as appropriate. Moreover adverse events will be described by MedDRA's System Organ Classes (SOCs) and Preferred Term (PT).

Similar summary tables will be provided for the number of AEs/SAEs at least possibly related to study treatment and for the number of AEs/SAEs leading to study discontinuation.

The number and percentage of subjects with AEs/SAEs will be summarized by their MedDRA preferred term within SOC.

Any subject reporting multiple episodes of the same AE/SAE (i.e. same preferred term) will be counted once.

Compliance will be calculated as the percentage of medication taken in relation to the recommended dose and the actual period of treatment (number of doses reported to be taken / number of doses envisaged x 100). Treatment Compliance will be described by means of descriptive statistics.

The number of subjects who need a dose re-adjustment during the long-term follow-up phase of the study will be compared between treatment groups by means of Chi test.

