9.2 PATIENT DISPOSITION

A complete screening disposition on screened subjects including the number of enrolled subjects, randomized subjects, screening failures and the reasons for screening failure will be provided.

Summary table of not met inclusion and exclusion criteria will also be provided.

A study disposition table on randomized subjects will be provided and it will include number of subjects who completed or discontinued the study and reasons for discontinuation.

Dispositions of randomized subjects who performed each visit and number of patients included in each analysis population will be provided too.

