10.1 Tolerability parameters

10.1.1 Adverse Events

The total number and percentage of subjects with at least one Adverse Event (AE), treatment-emergent Adverse Event, serious Adverse Event, drug-related Adverse Event, Adverse Event leading to treatment discontinuation and Adverse Event leading to death will be summarized by treatment group.

The following summary tables by treatment group will also be provided:

- Adverse Events by System Organ Class (SOC) and Preferred Term (PT);
- Serious Adverse Events by System Organ Class (SOC) and Preferred Term (PT);
- Treatment-Emergent Adverse Events by System Organ Class (SOC) and Preferred Term (PT);
- Drug related Treatment-Emergent Adverse Events by System Organ Class (SOC) and Preferred Term (PT);

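### The SAP replaces the protocol's adverse events leading to study discontinuation with events leading to drug withdrawal, without declaring the change, and can miss children who leave for an adverse event while LT4 continues

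*SAP*

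**What the plan says.** **Protocol.** Section 19.3.4 asks for summary tables "for the number of AEs/SAEs leading to study discontinuation", alongside those for all events and for events at least possibly related to treatment. Section 14.1 sets out how an AE ends participation: it is an event, including onset or worsening of a concomitant illness, "that is considered by the PI to be incompatible with continuation in the study". That criterion does not mention stopping LT4. Section 16.2.15 says that at the end-of-study visit "the PI will prescribe the appropriate LT4 product to allow continuation of TH therapy". Section 13.1.2 requires that infants already on LT4 enter the trial without a gap in treatment.

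**SAP.** Section 4 gives a single criterion: "Adverse Events leading to discontinuation is an AE with action taken equal to" *Drug withdrawn*. Section 10.1.1 plans one overview line for it, worded "Adverse Event leading to treatment discontinuation and Adverse Event leading to death will be summarized by treatment group". None of the four tables by System Organ Class and Preferred Term in that section covers discontinuation. Section 9.2 separately plans a disposition table with the "number of subjects who completed or discontinued the study and reasons for discontinuation". Section 3.4, which lists changes from the protocol, covers protocol 19.2, 19.3.1, 19.3.2 and 19.3.3 only. It has no entry for 19.3.4.

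**The concern.** The protocol's outcome depends on whether an AE took the child out of the study. The SAP's outcome depends on what was done with the drug. In many trials the two nearly coincide, because leaving the trial means stopping the trial drug. Here both arms receive the same hormone as replacement therapy, and that therapy is expected to carry on when trial participation ends. The two events can therefore separate, and the SAP's criterion would then miss the event that the protocol asked for.

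At stake is whether the study report can say which AEs, of what seriousness and relatedness, caused children to leave. A reader of the AE table could also find no event leading to discontinuation while the disposition table shows a child who left because of one, with nothing in the SAP to explain the difference. Because the change is undeclared, that reader would not know that the outcome had been redefined.

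**Working it through.** The plan states no figure on this point, so there is nothing to reproduce. The check compares definitions and then works out what one child is worth.

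**1. The two definitions.** Let S mean that an AE caused the child to leave the study (protocol 14.1 and 19.3.4). Let W mean that the action taken for the AE is recorded as *Drug withdrawn* (SAP 4).

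| | W | not W |
|---|---|---|
| S | counted by both | counted by the protocol, missed by the SAP |
| not S | counted by the SAP only | counted by neither |

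The definitions agree only if the off-diagonal cells are empty.

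**2. Can S occur without W?** Protocol 14.1 makes S depend on the investigator's view of continuing in the study. Protocol 13.1.2 and 16.2.15 show that replacement is meant to go on at entry and after the end of study. A child with an intercurrent illness that makes trial participation unworkable can leave while LT4 continues. In the control arm, infants keep the tablets they were prescribed before the trial, which the sponsor does not supply (protocol 13.1.1). In the Tirosint-SOL arm, the product is commercially available (protocol 8.1) and could also continue. So the cell S without W can be occupied in either arm.

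**3. Does another SAP output recover the missing information?** In part. The 9.2 table should show the exit and its reason. As described, it does not carry the AE's term, seriousness or relatedness, which the AE/SAE tables in protocol 19.3.4 are meant to give.

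**4. Is the change declared?** No. SAP 3.4 has no entry for protocol 19.3.4.

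**5. What one uncounted child is worth.** SAP section 3 gives 31 randomized children, and SAP 3.3 gives 2:1 allocation. The total per arm is not stated, so 21:10 is assumed (31 × 2/3 = 20.7), with 20:11 and 22:9 as the range. The change in an arm's percentage is 100 × 1/n:

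| Assumed split (Tirosint-SOL : tablets) | Tirosint-SOL arm | Tablet arm |
|---|---|---|
| 20:11 | 1/20 = 5.0 points | 1/11 = 9.1 points |
| 21:10 | 1/21 = 4.8 points | 1/10 = 10.0 points |
| 22:9 | 1/22 = 4.5 points | 1/9 = 11.1 points |

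These figures show sensitivity to one child. The documents report no such exit.

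**The case against.** The strongest defence is that the SAP is consistent within itself. Section 10.1.1 says treatment discontinuation, *Drug withdrawn* is a direct way to identify that, and study exits have their own table in 9.2. Two tables that measure different things may differ without contradiction. This stands as a reason to keep the row. It does not supply the outcome that protocol 19.3.4 planned, and it does not explain why SAP 3.4 is silent.

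A second defence is that the code list and completion guidance for action taken are not shown. Tablets are handled as a within-study treatment: protocol 16.1 defines a first day of administration within the study for children staying on tablets, and SAP 10.1.4 takes the end date for compliance from the last study dose on the end-of-study form. A site might therefore record *Drug withdrawn* whenever within-study treatment ends. This also stands, and it limits the conclusion to saying that the rule *can* miss such exits.

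A reader might go further and infer that the loss falls mainly on the tablet arm, so that its rate is close to zero by construction and the comparison between arms is reversed. The documents do not support that. A child leaving the Tirosint-SOL arm could also continue the same commercial product and be missed, and nothing shows how sites would code either case. An example in which one child per arm leaves and only the tablet child goes uncounted assumes the asymmetry it is meant to show. A reader might also rest the argument on LT4 being lifelong, but the documents do not say so, and protocol 8.1 mentions transient forms of the disease. The argument needs only that therapy is meant to continue after the study.

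**Conclusion.** The point holds as an undeclared change of a planned safety outcome, made with a rule that can undercount that outcome. The change itself is evident from protocol 19.3.4 read against SAP 3.4, 4 and 10.1.1, and needs no assumption about data or sites. The undercount is a possibility. It requires a child who leaves for an AE while LT4 continues, and a site that does not code the event as *Drug withdrawn*. Under the assumed split of about 21:10, each such child is worth about 5 points in the Tirosint-SOL arm or 10 points in the tablet arm. Neither the number of such children nor the direction of any bias can be determined from the documents.

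The importance is moderate. The row is descriptive and untested, and AEs are not named among the objectives in SAP 3.1. With 31 children, however, a single exit for an AE is worth reporting in full, and the SAP as written does not ensure this.

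**What to change.** 1. In SAP 4 and 10.1.1, keep the *Drug withdrawn* criterion and name it consistently as AEs leading to treatment discontinuation.
2. Add a separate definition and row by arm for AEs/SAEs leading to study discontinuation, meaning events recorded as the reason for leaving under protocol 14.1. Show serious events separately, and list term, seriousness and relatedness for each child concerned.
3. Reconcile the new row with the 9.2 disposition table. If the recorded reason says only that an AE occurred, identify the event from the child's AE records before the tables are produced, and state how this was done.
4. Record in SAP 3.4 any remaining departure from protocol 19.3.4, with the reason.

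The cost is a few sentences in the SAP, one table row and a short listing. Reasons for discontinuation are already planned for tabulation under SAP 9.2, so no new data collection should be needed.

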4.1 BASELINE DEFINITION

Unless stated otherwise, baseline will be defined for each subject as the last non-missing measurement (scheduled or unscheduled) obtained prior to the treatment start date.

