## 7.1 SCHEDULE OF EVALUATIONS (SOE)

**Table 1 Schedule of Evaluations**

Visit	V1	Treatment start	V2	V3	FU1 a	V4	V5	V6	V7	V8	V9	V10	V11	FU2 b
Age at Visit	Varies		Varies	Varies		2 months (60 days $\pm 7$ )	4 months (120 days $\pm 14$ )	6 months (180 days $\pm 14$ )	9 months (270 days $\pm 14$ )	12 months (365 days $\pm 21$ )	15 months (455 days $\pm 21$ )	18 months (545 days $\pm 21$ )	21 months (635 days $\pm 21$ )	
Study Day	-14/1 c	1	8-15 d	22-29 d		Varies d	Varies d	Varies d	Varies d	Varies d	Varies d	Varies d	Varies d	
Phase			TFTs normalization phase			Long-term follow-up phase								
Visit Type	Clinic		TM	Clinic	TM	TM	Clinic	Clinic	Clinic	Clinic	Clinic	Clinic	Clinic	TM
Informed Consent	X													
Demographics	X													
Medical History	X													
Concomitant Medications	X		X	X	X	X	X	X	X	X	X	X	X	X
Eligibility	X													
Adverse Events	X		X	X	X	X	X	X	X	X	X	X	X	X
Randomization	X c													
Physical Exam e	X			X			X	X	X	X	X	X	X	
Signs and symptoms of hypo- and hyper-thyroidism	X		X	X	X	X	X	X	X	X	X	X	X	X
Body Measurements f	X			X			X	X	X	X	X	X	X	
Nutritional Intake	X		X	X	X	X	X	X	X	X	X	X	X	X

a Subjects who at V3 have not yet achieved TFTs normalization will undergo one or more additional follow-up visits at appropriate time intervals (usually every 2 weeks) until TFTs are normalized (e.g. Follow-Up Type 1, FU1). If the timing of FU1 visit overlaps with the next planned visit (V4-V8), it is possible to perform only the planned visit.

b After V4, if a dose adjustment is needed or, at Investigator's judgement, if an abnormal T4 or TSH are found, additional follow-up visit(s) (2-6 week intervals) should be performed until normalization occurs (e.g. Follow-Up Type 2, FU2). If the timing of FU2 visit overlaps with the next planned visit (V5-V11), it is possible to perform only the planned visit.

c The procedures of screening and inclusion at V1 may be spread over multiple days (particularly when laboratory results need to be collected), but should be completed within 2 weeks with Randomization on Day 0 or 1. Day 1 is the first day of study drug administration (for subjects continuing on tablets, the first day of drug administration within the study).

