d The procedures conducted at each visit may take place on multiple days (0-7 days) all within the allowed time frame.

e Including standard health maintenance exam for age and vital signs (Heart Rate and Temperature).

f Including length, body weight (BW) and head circumference.

Visit	V1	Treatment start	V2	V3	FU1 a	V4	V5	V6	V7	V8	V9	V10	V11	FU2 b
Age at Visit	Varies		Varies	Varies		2 months (60 days ±7)	4 months (120 days ±14)	6 months (180 days ±14)	9 months (270 days ±14)	12 months (365 days ±21)	15 months (455 days ±21)	18 months (545 days ±21)	21 months (635 days ±21)	
Blood Sampling for TFTs g	X h		X m	X	X	X	X	X	X	X	X	X	X	X
Dosing Evaluation	X		X	X	X	X	X	X	X	X	X	X	X	X
eDiary dispensing and instruction	X													
Treatment														
Daily eDiary														
CareCAT i			X	X		X	X	X	X	X				
Parents' Satisfaction Questionnaire j	X			X			X	X	X	X	X	X	X	
Subject Visit Reminder Card	X			X			X	X	X	X	X	X		
Drug dispensing and instruction k	X			X			X	X	X	X	X	X		
Drug return				X			X	X	X	X	X	X	X	
Treatment compliance			X	X	X	X	X	X	X	X	X	X	X	X
End of Study l										X	X	X	X	

g May be collected at the study visit or prior (0-7 days) to the study visit, within the visit allowed time frame.

b Subject's own lab results are acceptable. For newly diagnosed neonates, the lab results obtained from routine diagnostic workup will be recorded at V1; labs do not need to be repeated at Screening Visit for the purpose of the study. For infants who are already on TH therapy, the lab results obtained during routine follow-up will be recorded at V1, if not older than 4 weeks (<28 days); blood will be collected and analyzed if a lab report dated less than 28 days is not available, or if necessary as per Investigator's medical judgement.

i CareCAT will be completed after the daily drug administration in the eDiary during the first week of treatment (on days 1-7), during the third week of treatment (on days 15-21), and during the eighth week of treatment (on days 50-56).

j Parents' Satisfaction Questionnaire will be completed in the eDiary at V1 only for infants who are already on TH therapy and 0-3 days prior to all other in-clinic visits for all subjects.

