## 16.1 SCREENING/INCLUSION (RANDOMIZATION) – VISIT 1 (DAY -14 to 1)

The procedures of screening and inclusion may be spread over multiple days (particularly when laboratory results need to be collected), but should be completed within two weeks.

If a subject is found to be potentially eligible for the trial, parents/legal guardians will be informed both verbally and in writing about the study objectives and procedures. The Informed Consent Form (ICF) will be signed and dated by the parents/legal guardian and the PI. The informed consent process must be documented in the medical record of the subject.

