### **AE collection and reporting should begin after informed consent is given.**

After informed consent to participate in the study has been obtained, the neonate/infant will be assigned a Subject Number and the PI or designee will do the following to confirm eligibility:

- Record demographic data and medical history; and
- Record prior and concomitant medications;
- Verify compliance with the inclusion/exclusion criteria.

If eligibility for the trial is confirmed, the PI or designee will do the following:

- Perform a physical examination including body measurements and vital signs;
- Assess the presence of signs and symptoms of hypo- or hyper- thyroidism;
- Record nutritional intake;
- Record results of TSH, FT4 and/or TT4 from original diagnosis from medical records (both results from dried spot whole blood, if available, and from confirmatory serum tests, specifying if results are expressed per unit of blood or per unit of serum);
- Take blood samples for serum TSH, FT4 and, optional, TT4 (for infants who are already on TH therapy and for whom a lab report dated < 28 days is not available) or record results of TSH, FT4 and TT4 (for infants who are already on TH therapy and for whom a lab report dated < 28 days is available; in this latter case a blood draw and re-assessment of hormonal values can be done, if necessary as per Investigator's medical judgement);
- Randomize the subject using the IWRS (Day 0 or Day 1 of the study);
- Perform dosing evaluation;
- Dispense the assigned drug product;
- Instruct parents/guardians about drug product administration and indicate the date of the first dose to be administered;
- Verify with parents/guardians that they can access and how to use the eDiary including instruction on how to perform and timelines of the:
  - Drug administration;
  - CareCAT;
  - Parents' Satisfaction Questionnaires;

- Ask parents/guardians to complete the Parents' Satisfaction Questionnaire in the eDiary (for infants already on LT4 therapy); and
- Complete and provide parents/ guardians with the Subject Visit Reminder Card.

The **first day of study drug administration (Day 1)** (for subjects continuing on tablets, the first day of drug administration within the study) should be either the same day of randomization (preferred) or the day after.

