9.4.2 Secondary efficacy analyses

Laboratory parameters (TSH and FT4)

Laboratory parameters (TSH and FT4) will be analysed at each time point by means of analysis of covariance (mixed model), including basal value, treatment group, age at randomization and interactions between visit and treatment group as covariate.

Normal distribution for TSH and FT4 will be tested with Shapiro Wilks, if data result not to be distributed as a normal distribution a log transformation will be applied.

The mixed model will be adjusted with Kenward-Roger method and the unconstructed covariance matrix will be used as first choice (other matrixes will be considered if there will be convergence problems).

Summary descriptive statistics will be provided for each laboratory parameter. TSH and FT4 levels at each visit will also be compared between treatment groups by Wilcoxon Mann-Whitney test. This analysis will also be repeated stratified on neonates and infants.

Laboratory data will also be listed with clinically significant information.

TSH values above 4.5 mU/L

The events of TSH values above 4.5 mU/L will be compared between treatment groups at each visit and aggregate from Visit 2 to the last available visit using a Chi-squared test or, when the expected values in any of the cells of a contingency table are below 5 or the total number of observations is less than 20, Fisher exact test as appropriate.

FT4 values below the middle of the laboratory normal range

The events of FT4 values below the middle of the laboratory normal range will be compared between treatment groups at each visit and aggregate from Visit 2 to the last available visit using a Chi-squared test or, when the expected values in any of the cells of a contingency table are below 5 or the total number of observations is less than 20, Fisher exact test as appropriate.

Parent satisfaction assessed by “Parents’ Satisfaction Questionnaire”

Parent satisfaction assessed by “Parents’ Satisfaction Questionnaire” score at V3, V5, V6, V7, V8, V9, V10, V11 will be analyzed by means of analysis of covariance (mixed model), including treatment age at randomization and interactions between visit and treatment group as covariate.

Normal distribution for Parents’ Satisfaction Questionnaire score will be tested with Shapiro Wilks, if data results not be distributed as a normal distribution a log transformation will be applied.

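### The SAP's date-only baseline rule rejects a pre-dose TSH/FT4 sample drawn on Day 1, which can give an infant an outdated or missing basal value in the TSH and FT4 mixed models

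*SAP*

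**What the plan says.** SAP Section 4.1 sets baseline, unless stated otherwise, as "the last non-missing measurement (scheduled or unscheduled) obtained prior to the treatment start date". It makes no allowance for a sample taken earlier on the treatment start date itself.

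In Protocol Section 16.1, Visit 1 runs from Day -14 to Day 1, and its procedures "may be spread over multiple days (particularly when laboratory results need to be collected"). Table 1 adds that they "should be completed within 2 weeks with Randomization on Day 0 or 1". Day 1 is the first day of study dosing and, by Section 16.1, "should be either the same day of randomization (preferred) or the day after".

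The source of the Visit 1 hormone values depends on the child:
- Neonates starting LT4: "the lab results obtained from routine diagnostic workup will be recorded at V1; labs do not need to be repeated at Screening Visit" (Table 1 footnote).
- For infants already on LT4, "the lab results obtained during routine follow-up will be recorded at V1, if not older than 4 weeks (<28 days"). Blood is drawn at Visit 1 only if there is no such report, or if the investigator judges a repeat necessary.
- For all children, Section 16.1 also tells the site to "Record results of TSH, FT4 and/or TT4 from original diagnosis from medical records".

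SAP Section 9.4.2 fits mixed models to TSH and FT4, "including basal value, treatment group, age at randomization" and the visit-by-treatment interaction. SAP Section 8 states that missing values are not replaced.

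**The concern.** The two documents use Day 1 differently. In the protocol, Day 1 is the last day of Visit 1 and may hold a blood draw, randomization and the first dose, in that order. In the SAP, anything dated on the treatment start date is too late to be baseline. A sample taken exactly as the protocol allows, before the first study dose, can therefore be discarded.

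What replaces it is left open. Section 4.1 has no look-back limit and does not say whether a value from the CH diagnosis is eligible. For an infant who has been on LT4 for weeks or months, that value describes the untreated state and is a poor basal value for on-treatment TSH or FT4. If it is ruled out and nothing else exists, the child has no covariate value and drops out of the model.

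SAP version 2.0 removed the neonate/infant term and center from the models (SAP Section 3.4). Basal value and age at randomization are the only baseline adjusters left, so the model cannot absorb a mix of untreated and on-treatment basal values through that term. The trial is also open-label: enrolment closed on 31 March 2024 and the final SAP is dated 24 March 2026. A choice left to programming would be made with treatment assignments known.

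**Working it through.** The plan gives no figure to reproduce. The check is a comparison of dates, followed by a count of who could be exposed.

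**Step 1. Is the rule about dates or times?** Section 4.1 refers to the treatment start date and mentions no clock time. SAP Section 4 classifies previous medications and pre-treatment adverse events by the same strict comparison of dates. The literal reading is therefore: sample date < date of first study dose.

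**Step 2. Apply that rule to each route by which a basal TSH/FT4 can arise.**

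| Situation | Result under SAP 4.1 |
|---|---|
| Neonate, diagnostic work-up dated before Day 1 | Kept, and the right value |
| Infant, routine report under 28 days old, no Visit 1 draw | Kept |
| Infant, Visit 1 draw before Day 1 (including Day 0 with dosing next day) | Kept |
| Infant, report under 28 days old plus a repeat draw on Day 1 | Day 1 value rejected; older follow-up report used |
| Infant, no recent report, only recent draw on Day 1 | Day 1 value rejected; falls back to the diagnosis value or another older one, or is missing |

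Only the last two rows are harmed, and only the last row seriously. An edge case is a neonate whose confirmatory serum is drawn on the day of the first dose; at most 4 children could be in that position.

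**Step 3. Which analyses use a basal value?** (SAP Sections 9.4.1 and 9.4.2)
- TSH and FT4 mixed models: yes.
- LT4 dose/kg and questionnaire mixed models: no basal term.
- Visit-wise Wilcoxon tests of TSH and FT4: no.
- TSH and FT4 threshold events (Chi-squared or Fisher): no.
- Growth (Wilcoxon at each visit): no.

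**Step 4. How many children could be affected?** SAP Section 3 gives 31 randomized; SAP Section 3.4 gives 3 + 1 = 4 neonates. Infants: 31 − 4 = 27, and 27/31 = 87%. The documents do not say how many infants had a Day 1 draw, so the share p is an assumption:

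| Assumed p | Infants (27 × p) | Share of 31 |
|---|---|---|
| 0% | 0 | 0% |
| 10% | 2.7 | 9% |
| 25% | 6.8 | 22% |
| 50% | 13.5 | 44% |
| 100% | 27 | 87% |

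These counts cover both harmed rows of Step 2. Each child is 1/31 = 3.2% of the sample.

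**Step 5. How far off could a diagnosis value be?** For illustration only: Protocol Section 8.1 cites a screening TSH above 40 mIU/L as the level for immediate treatment, and Section 11.3.1 cites an on-treatment target below 5 mU/L. The ratio at those limits is 40/5 = 8. The protocol sets no TSH cut-off and admits normal FT4 at diagnosis, so the gap would be smaller in mild disease.

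**The case against.** The best counter-argument is that the protocol's own workflow makes the bad case rare. Most infants should arrive with a routine report under 28 days old, which normally predates Day 1 and is kept. Where a draw is needed, the dose at inclusion depends on its result, and Protocol Section 22.1 allows 24 to 72 hours for testing. Section 16.1 lets Visit 1 extend over several days for this reason. Such a draw would therefore often precede Day 1. This stands as a reason to expect few cases, but nothing in the protocol rules out a Day 1 draw.

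It can also be said that SAP Section 9.3 lists TSH and FT4 at CH diagnosis and at screening as separate variables, so the diagnosis value would not be mistaken for baseline. This stands in part: the SAP does tell them apart in its tables. It does not say which one feeds the basal covariate, and the Section 4.1 rule, applied as written, could select the diagnosis value. The table and the model could then show different baselines for the same infant.

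A reader might infer more than the documents support, in three ways:
- That Visit 1 assessments are rejected in general. They are not: the preferred dosing day is tied to randomization, at the end of a window of up to two weeks, and values dated earlier remain eligible.
- That every infant with a Day 1 draw is lost or given an untreated value. An infant with a recent report falls back to that report.
- That a discarded Day 1 weight does damage. No dose/kg or growth analysis uses a basal value, and the baseline tables are specified at screening.

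**Conclusion.** The conflict is real but narrow. As written, SAP Section 4.1 excludes a pre-dose TSH or FT4 sample drawn on Day 1, although the protocol permits that timing and prefers dosing on the randomization day. The result is an older follow-up value for some infants. For those with no other recent sample, it is an untreated diagnosis value or no basal value at all. Since diagnosis values are recorded at Visit 1, mis-assignment is likelier than outright loss.

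The number affected cannot be derived from the documents. The range of 0 to 27 infants is a bound, not an estimate, and its upper end assumes a Day 1 draw in every infant. The conclusion also rests on the literal, date-only reading of the rule.

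It would be wrong to infer that the trial's main comparison is at risk. LT4 dose/kg, the SAP's primary variable, is untouched; TSH and FT4 are secondary, are also compared by tests that use no baseline, and all efficacy analyses are labelled exploratory (SAP Section 9.4). Severity: minor to moderate, not a must-fix.

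**What to change.** Amend SAP Section 4.1 to say three things:
1. Baseline is the latest available value obtained on or before the treatment start date and before the first study dose.
2. A Visit 1 sample dated Day 1 with no recorded time is treated as pre-dose unless there is evidence that it was taken after the dose.
3. For infants already on LT4, the TSH and FT4 from the CH diagnosis are not used as the basal value. This agrees with the separate screening and diagnosis variables in SAP Section 9.3.

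Simply declaring every Visit 1 assessment to be baseline would be too loose, because it could admit a Day 1 sample taken after the dose.

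The report should also state how many infants had their basal sample on Day 1 and how many have no basal value, by arm. The cost is a few sentences in the SAP and one line of reporting; no new data are needed.
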